# **Study duration**

The projected time frame for this research project is from May 2017 to May 2018. The recruitment and

treatment of patients with 60 teeth matching the inclusion criteria mentioned above can be reasonably achieved within these 12 months. Included patients will not participate in this proposed study longer than the time necessary for the routine root canal therapy.


# Characteristics of the Study Population

#### **Target population**

Patients presenting to the Department of Endodontics, School of Dental Medicine, University of Pennsylvania for evaluation and routine endodontic treatment of infected, necrotic teeth with chronic apical periodontitis.

**Subjects enrolled by Penn Researchers** 

Subjects enrolled by Collaborating Researchers

0

#### Accrual

Patients will be treated in the Endodontic Clinic of the University of Pennsylvania's Department of Endodontics of the School of Dental Medicine (PDM). The Endodontic Clinic exclusively handles all root canal procedures carried out at the PDM, with the exception of Dental Care Network facilities. By

postgraduate residents alone, more than 1500 root canal procedures are done routinely per year. Patients are PDM patients coming from the Restorative Department of the PDM, emergency admissions or referred from outside private clinics directly to the clinic. The recruitment and treatment of patients with 60 teeth matching the inclusion criteria mentioned above can be achieved within a reasonable time. The clinical significance of this investigation will not be evaluated by statistical analysis based on overall sample size. A target negative culture threshold is well established in the literature for an acceptable success rate (refer to Background, reference 4) and the experimental and comparison groups are evaluated as successful (or unsuccessful) for their ability to reach this threshold (or not). Comparable studies investigating the reduction of intra-canal bacteria after changes in treatment protocol have been conducted with similar sample sizes (refer to Background, references 15-18).

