# Primary outcome variable(s)

Studies has shown that the bacteria within tooth root canal system is the primary etiology for the root- end disease process. The reduction or elimination of microorganisms from the root canal system of infected teeth has been shown to correlate with the long-term success of the endodontic treatment. The main objective of root canal treatment is to disinfect root canal systems entirely and seal to prevent further contamination. However, with current techniques, it is impossible to eradicate bacteria and biofilm completely from the complex root canal system. This study is designed to evaluate the antibacterial efficacy of Feraheme/H2O2 and to compare it to the routinely used protocol. The outcome

will be evaluated by taking bacterial samples from the root canals during routine root canal treatment after applying different disinfection protocols. Bacteria from each sample will be quantified. The primary outcome parameter will be the difference in bacterial reduction between the experimental group (Feraheme) and a comparison group (routinely used protocol).

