# **Background**

Endodontic research has established the importance of microorganisms in the pathogenesis of apical periodontitis (1-3). The reduction or elimination of microorganisms is a logical aim for successful endodontic treatment. Sjörgen et al (4) evaluated the long-term outcome after one step endodontic treatment of teeth with negative or positive cultures after instrumentation. 94% of the teeth filled after a negative culture succeeded, whereas only 68% of the canals filled after a positive culture had been detected were successful. Based on this study the optimal clinical success will be reached if a tooth is filled when the bacterial load of the canal is undetectable with culturing methods. Because culturing is as yet only effective as a research tool, the clinician should expect optimal success when treating an infected tooth with a technique or protocol that has been shown experimentally to result in consistent negative cultures. Byström et al (5-7) published a series of studies to evaluate the antibacteriological effects of the individual steps in the endodontic procedure. Only after instrumentation using endodontic instruments with NaOCl and EDTA irrigation and a dressing of calcium hydroxide it was possible to obtain a predictable negative culture (5-7). However, Histo-bacteriological studies have shown that even after meticulous chemomechanical preparation using endodontic instruments with NaOCl and EDTA and obturation of the root canal system, a significant amount of bacterial biofilm is often present in the anatomical complexities of the root canal system (isthmuses, apical ramification, accessory canals, and dentinal tubules) and on the walls of the main root canal that was not engaged by the root canal instruments (8-10). Endodontic biofilms may play a key role in infections persisting after primary or secondary endodontic treatment, as microorganisms growing in biofilms are better protected from adverse environmental changes and other antimicrobial agents. Ricucci et al, (11) evaluated the prevalence of bacterial biofilms in untreated root canals of teeth showing apical periodontitis in 80% of the cases. Nevertheless, the persistence of endodontic infections is also attributed to the presence of the aforementioned anatomical complexities, which can harbor biofilm and protect it from the effects of the current disinfection solutions (12). Based on these facts, advanced disinfection strategies with the ability to disrupt biofilm are needed to achieve the goal of endodontic treatment and to overcome the persistence of endodontic infections, if possible using less harsh chemicals as currently used (e.g. NaOCl). Hydrogen peroxide (H2O2) is commonly used as a safe green chemical (13) for disinfection purposes or as tooth-whitening agent (at concentrations as high as 10%) because it generates free radicals that exhibit antibacterial activity or stain removal (through degradation of polymeric substances). However, the process of free radical generation is slow and H2O2 by itself has a modest anti-biofilm or endodontic disinfection effects when used alone. It has been shown that catalytic iron oxide nanoparticles (CAT-NP) have enhanced peroxidase-like activity that catalyzes hydrogen peroxide (H2O2) to create a potent anti-biofilm action in vivo (14). Very low concentrations of CAT-NP (at 0.5 mg/ml) rapidly catalyze H2O2 to generate free radicals in situ that simultaneously degrade the biofilm matrix and kill embedded bacteria with exceptional efficacy within 5 minutes (5,000-fold more effective than H2O2 alone), without cytotoxic effects on oral tissues in vivo (14). Recently, in a preliminary in- vitro study we tested the antibacterial activity of CAT-NP/ H2O2 in comparison to 3% H2O2, 3% NaOCl, and 2% CHX, the latter two solutions are current disinfectants used in endodontic treatment. The solutions were topically placed on dentine blocks that were infected with E. faecalis, a commonly isolated microorganism from root canal treated teeth with persistent apical periodontitis. Our results show that the antibacterial activity of CAT-NP/H2O2 was significantly better than the conventional irrigants. CAT-NP/H2O2 was up to 30-fold more effective in bacterial killing compared to NaOCl and CHX. These results reveal the potential to exploit CAT-NP/H2O2 as a potent alternative approach for treatment of endodontic infections. Recently, an FDA-approved iron oxide nanoparticle formulation known as Feraheme became available commercially. Our in-vitro studies have shown that the peroxidaselike activity of Feraheme is similar to CAT-NP and this nanoparticle with H2O2 exhibited similar catalytic activity and potent anti-biofilm effects against endodontic biofilms. Feraheme is approved as an intravenous treatment for iron deficiency with repeated dosing at 510 mg. For

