#### **Analysis Plan**

After incubation the number of colony forming units will be determined by using a stereoscope. ANOVA and Students t-test will be used for statistical analysis.

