# **Potential Study Benefits**

The participant is not expected to get any personal benefit from taking part in this proposed research study. Microbial elimination is a key to the successful treatment of infected, necrotic teeth. Finding a better protocol to reduce intracanal infection will increase the successful outcome of endodontically treated necrotic, infected teeth and will result in an increased retention of natural teeth for the general population. The proposed study will verify by the means of microbial sampling and culturing, whether Feraheme/H2O2 irrigation protocol can provide better, effective disinfection on root canal surfaces and a significant reduction of intra-canal infection in-vivo. If this can be demonstrated by the proposed investigation it will have clinical significance as an improvement of root canal therapy.

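### The Accrual section's pass/fail verdict for each group has no stated bar, carries no uncertainty and does not measure a difference in culture-negative teeth

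*Combined protocol and SAP*

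**What the plan says.** The Accrual section gives a target of 60 teeth and then sets out its own way of judging clinical significance: "The clinical significance of this investigation will not be evaluated by statistical analysis based on overall sample size". It refers to a literature target for negative cultures, citing reference 4 of the Background, and states that "the experimental and comparison groups are evaluated as successful (or unsuccessful) for their ability to reach this threshold (or not".

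The Background is the only place where that target is described.
- For a single tooth, "the optimal clinical success will be reached if a tooth is filled when the bacterial load of the canal is undetectable with culturing methods".
- For a protocol, the aim is "a technique or protocol that has been shown experimentally to result in consistent negative cultures". No number is attached.
- From reference 4 it reports that "94% of the teeth filled after a negative culture succeeded, whereas only 68% of the canals filled after a positive culture" were successful.

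Elsewhere the plan is comparative. Under Primary outcome variable(s): "The primary outcome parameter will be the difference in bacterial reduction between the experimental group (Feraheme) and a comparison group (routinely used protocol". The Analysis Plan, after describing the colony count, says only that "ANOVA and Students t-test will be used for statistical analysis". Potential Study Benefits says the study will verify "whether Feraheme/H2O2 irrigation protocol can provide better, effective disinfection on root canal surfaces". The same sentence goes on to a significant fall in infection inside the canal, and the section then links such a result to clinical significance.

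The Design and Procedures sections describe three analysable samples: S1 before treatment, S2 after the assigned solution, and S3 after a further NaOCl irrigation given to every group.

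**The concern.** A verdict on a group needs a group-level bar, and none is stated. The per-tooth definition says when one culture is negative. It does not say how many teeth must be negative for a protocol to count as successful. The two percentages from reference 4 are treatment success rates by a tooth's culture status at filling, so they are not that bar either.

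Accrual also does not name the sample. S2 can be inferred, because it is the only post-treatment sample that isolates the assigned solution, but the section does not say so.

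Two things are at stake. First, whoever applies the rule must choose a proportion and a sample, possibly with the counts in view. Second, each verdict is a bare yes or no. It does not show how precisely the group's proportion is known, and a pair of verdicts does not estimate how far apart the groups are. No section plans a comparison of culture-negative proportions that would fill the gap.

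**Working it through.** **Plan's own figure.** The 60 teeth cannot be reproduced. The documents give no alpha, power, effect size, standard deviation, culture-negative rate or allocation ratio.

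**Inputs.**
- Teeth per arm (equal allocation assumed): 60/2 = 30 if there are two arms, as the assignment chart in Design says; 60/3 = 20 if there are three, as in Procedures.
- Group bar: not in the documents. Assumed at 60, 70, 80, 90 and 100%.
- One tooth per patient: assumed.

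**Rule tested.** A group passes if its number of culture-negative teeth X satisfies X ≥ bar × n.

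**Measures.** Two-sided Fisher exact p, and the Newcombe 95% interval for d = p1 − p2, built from the Wilson limits (l, u) of each proportion:
- lower = d − √[(p1 − l1)² + (u2 − p2)²]
- upper = d + √[(u1 − p1)² + (p2 − l2)²]

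**80% bar, 30 per arm** (pass mark 0.80 × 30 = 24).

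*Opposite verdicts, 24/30 vs 23/30.* Wilson limits are 0.627 to 0.905 and 0.591 to 0.882; d = 0.033.
- Lower = 0.033 − √(0.173² + 0.115²) = −0.17
- Upper = 0.033 + √(0.105² + 0.176²) = +0.24
- Fisher p = 1.00

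*Both fail, 23/30 vs 14/30.* Wilson limits are 0.591 to 0.882 and 0.302 to 0.639; d = 0.300.
- Lower = 0.300 − √(0.176² + 0.172²) = +0.05
- Upper = 0.300 + √(0.115² + 0.165²) = +0.50
- Fisher p = 0.033

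**Other assumed bars.** Every one-tooth split below has Fisher p = 1.00. The other columns give an example pair with p < 0.05 and its p-value.

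| n per arm | Bar | One-tooth split | Both fail | Both pass |
|---|---|---|---|---|
| 20 | 60% | 12 vs 11 | 11 vs 4 (0.048) | 19 vs 12 (0.020) |
| 20 | 70% | 14 vs 13 | 13 vs 5 (0.025) | 20 vs 14 (0.020) |
| 20 | 80% | 16 vs 15 | 15 vs 7 (0.025) | none |
| 20 | 90% | 18 vs 17 | 17 vs 10 (0.041) | none |
| 20 | 100% | 20 vs 19 | 19 vs 13 (0.044) | none |
| 30 | 60% | 18 vs 17 | 17 vs 8 (0.035) | 26 vs 18 (0.039) |
| 30 | 70% | 21 vs 20 | 20 vs 11 (0.038) | 28 vs 21 (0.042) |
| 30 | 80% | 24 vs 23 | 23 vs 14 (0.033) | 30 vs 24 (0.024) |
| 30 | 90% | 27 vs 26 | 26 vs 18 (0.039) | none |
| 30 | 100% | 30 vs 29 | 29 vs 22 (0.026) | none |

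One-tooth splits, and large differences hidden behind two failures, occur at every bar tried. Large differences hidden behind two passes occur only at the lower bars.

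**Detection limit for a negative culture.** The undiluted plate receives 0.25 ml, so one colony corresponds to 1/0.25 = 4 CFU per ml of transport fluid. This limit is nominal: at a true 4 CFU/ml the expected count is 1, and under Poisson sampling the plate is empty with probability e⁻¹ = 37%.

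**Power of a direct comparison.** For assumed rates of 70% vs 50%, exact Fisher power at two-sided 0.05 is 16% with 20 per arm and 26% with 30 per arm.

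**The case against.** An absolute benchmark is a legitimate thing to report, and it need not answer a comparative question. Two groups that both miss a bar have been correctly described as missing it. This stands, and it is why a benchmark may be kept if it is properly specified.

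A reader might go further and infer that the plan cannot support its claim of better disinfection at all. The documents do not support that. Potential Study Benefits never mentions the threshold or the verdicts. Its full sentence, with its reference to a significant fall in infection, fits the planned comparison of bacterial reduction, which may itself support the comparative wording. Nor does any section say that a pass against a fail shows superiority; that use of the verdicts would be a misuse, not a stated plan.

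It can also be said that any cut-off can be straddled by one tooth, and that the bar, rates and allocation above are assumed. This is true. The figures illustrate how such a rule behaves and do not predict this trial's result.

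Reference 4 itself may contain a group-level target, and the Background's call for consistency may mean that nearly all teeth should be negative. The source cannot be checked here. What can be said is that the plan neither reproduces such a target nor puts a number on consistency.

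Finally, the opening sentence in Accrual might only be declining a formal sample-size calculation. Even so, the verdicts that follow are the only method the section offers for judging the groups on culture status.

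**Conclusion.** The point holds within limits. The rule in Accrual cannot be applied as written, because neither the group bar nor the sample is stated. Any bar could be set after the counts are known. The verdicts carry no uncertainty and estimate no difference.

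The size can only be illustrated. At an assumed 80% bar with 30 per arm, a 3-point difference can split the verdicts and a 30-point difference can leave them the same. No probability of either event is claimed. The calculations assume equal allocation and one tooth per patient.

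The problem is confined to the culture-negative conclusion in Accrual. The primary between-group comparison of bacterial reduction, with its ANOVA and t-test, is unaffected. It would also be wrong to take 94% as the missing bar: as the Background describes it, that is the success rate among teeth filled after a negative culture, not the share of teeth that should be negative.

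**What to change.** In Accrual, replace the pass/fail verdicts with a secondary endpoint for estimation only:

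- **Endpoint:** the proportion of S1-culture-positive teeth with no colony on the 0.25 ml undiluted S2 plate (nominal detection limit 4 CFU per ml of transport fluid).
- **Reporting:** each arm's proportion with a 95% CI, and the Feraheme/H2O2 minus NaOCl risk difference with a Newcombe 95% CI. A Fisher exact p is optional.
- **Other teeth and arms:** report S1-negative teeth by arm. Give the saline proportion descriptively if that arm is used; the two-arm and three-arm descriptions in Design and Procedures need to be reconciled in any case.
- **Unit:** one tooth per patient, or an interval that allows for clustering if a patient contributes more than one.
- **Link to the rest of the plan:** state how this endpoint relates to the primary outcome and the Analysis Plan, and do not convert S2 or S3 status into the 94% and 68% success rates, which refer to culture status at root filling.

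If the investigators prefer to keep an absolute benchmark, they should name S2 and fix and justify the required proportion before any counts are known. Each arm's proportion should then be reported with a 95% CI against it, as description only and not as evidence that one protocol is better.

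**Cost.** The change is wording plus one small analysis on samples already planned. The simple pass/fail statement is lost or becomes descriptive, and the interval will be wide. Power is low (16% to 26% in the example above, and lower still if S1-negative teeth drop out), so the result should be read as an estimate and not as a confirmatory test.

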# Key inclusion criteria

Gender is not an inclusion or exclusion criteria. Patients will be eligible to participate in the study if the following inclusion criteria are met: 1. Patients to welling to participate in the study. 2. Patients are 18 years or above. 3. Non-contributory medical history (Patient can be seen for regular dental appointment in PDM; ASA classes I and II). 4. Tooth requiring root canal treatment with radiographic presence of periapical radiolucency and responding to thermal sensitivity testing negatively (difluordichlormethane at 50 °C) (Endo-Ice, Coltène/Whaledent Inc., Cuyahoga Falls, Ohio) and Negatively to EPT testing. 5. Tooth with adequate remaining tooth structure for proper isolation with rubber dam. 6. No history of previous endodontic treatment on the tooth. 7. Teeth with single canal and single and roots with single canals in multirooted teeth.

# Key exclusion criteria

Economic status, gender, race or ethnicity are not of concern for the proposed investigation and therefore for study exclusion. The cut-off age of 18 years was only chosen so as to limit the need for parental consent. Patients will not be eligible to participate in the study if any of the following exclusion criteria applies: 1. Self-reported Pregnancy. 2. Patients requiring antibiotic premedication prior to dental treatment. 3. Patients with multiple drug allergies. 4. Patients with known hypersensitivity to Ferumoxytol nanoparticles or any iron products. 5. Patients who are scheduled for MRI for the head region within three months after Fer nanoparticles application. 6. Periodontal changes (pockets 3 mm, mobility Grade I or gingival edema). 7. Radiographic presence of resorptive processes. 8. Cracked and fractured teeth. 9. if one of the inclusion criteria is not met.

# **Vulnerable Populations**

**Children Form** 

Pregnant women (if the study procedures may affect the condition of the pregnant woman or fetus) Form

Fetuses and/or Neonates Form

**Prisoners Form** 

Other

x None of the above populations are included in the research study

#### The following documents are currently attached to this item:

There are no documents attached for this item.

# Populations vulnerable to undue influence or coercion

Given the nature of the suggested study and the non-invasive procedures (irrigation within the closed environment of root canal, procedure of taking bacterial samples from a root canal) none of the potential participants appear to be likely to be vulnerable to coercion or undue influence or influence. Potential participants will receive the elected root canal treatment if they are participating in the study or if they are not participating in the study. In the event that Penn students or employees present for screening they will be informed that their decision regarding whether or not to participate will in no way impact their standing at the university. Given the number of patients seen on a regular basis in the Department of Endodontics and the common nature of the diseases pulp necrosis with apical periodontitis undue influence or coercion is not likely.

#### Subject recruitment

Patients presenting to the Department of Endodontics, School of Dental Medicine (PDM), University of Pennsylvania for evaluation and routine endodontic treatment of infected, necrotic teeth with chronic apical periodontitis will be asked to take part in the study if they meet the inclusion criteria specified above. Patients will be asked if they were interested to participate in this investigation after a clinical diagnosis matching is confirmed and the patient/ tooth meets the inclusion criteria specified above. Initial clinical diagnosis will be made by a postgraduate resident and verified by the supervising faculty. The PI, a full-time faculty, and the co-investigator, endodontic resident, will be informed about a potential study participant, verify the diagnosis and ask for participation (including consent and alternatives). No additional recruitment materials, such as radio/video scripts, flyers, internet postings, etc. will be used. No non-registered PDM patients will be asked to participate in the study.

Will the recruitment plan propose to use any Penn media services (communications, marketing, etc.) for outreach via social media avenues (examples include: Facebook, Twitter, blogging, texting, etc.) or does the study team plan to directly use social media to recruit for the research?

#### The following documents are currently attached to this item:

There are no documents attached for this item.

# **Subject compensation\***

Will subjects be financially compensated for their participation?

#### The following documents are currently attached to this item:

There are no documents attached for this item.

If there is subject compensation, provide the schedule for compensation per study visit or session and total amount for entire participation, either as text or separate document

N/A

